5.3 Exclusion Criteria

1. Disease Target Exclusion

- a) Patient has a history of basilar migraine or hemiplegic migraine

2. Medical History and Concurrent Diseases

- a) Patient history of HIV disease
- b) Patient history with current evidence of uncontrolled, unstable or recently diagnosed cardiovascular disease, such as ischemic heart disease, coronary artery vasospasm, and cerebral ischemia. Patients with Myocardial Infarction (MI), Acute Coronary Syndrome (ACS), Percutaneous Coronary Intervention (PCI), cardiac surgery, stroke or transient ischemic attack (TIA) during the 6 months prior to screening.
- c) Uncontrolled hypertension (high blood pressure), or uncontrolled diabetes (however patients can be included who have stable hypertension and/or diabetes for 3 months prior to being enrolled)
- d) Patient has a current diagnosis of major depression, other pain syndromes, psychiatric conditions (e.g., schizophrenia), dementia, or significant neurological disorders (other than migraine) that, in the Investigator's opinion, might interfere with study assessments
- e) Patient has a history of gastric, or small intestinal surgery, or has a disease that causes malabsorption

- f) The patient has a history or current evidence of any significant and/or unstable medical conditions (e.g., history of congenital heart disease or arrhythmia, known suspected infection, hepatitis B or C, or cancer) that, in the investigator's opinion, would expose them to undue risk of a significant adverse event (AE) or interfere with assessments of safety or efficacy during the course of the trial
 - g) History of, treatment for, or evidence of, alcohol or drug abuse within the past 12 months or patients who have met DSM-V criteria[15] for any significant substance use disorder within the past 12 months from the date of the screening visit
 - h) Patients should be excluded if they have a positive drug screen for drugs of abuse that in the investigator's judgment is medically significant, in that it would impact the safety of the patient or the interpretation of the study results. In addition:
 - i) Detectable levels of cocaine, amphetamine, and phencyclidine (PCP) in the drug screen are exclusionary. Patients who are positive for amphetamines on the urine drug screen may have their urine samples evaluated for further analysis at the investigator's discretion to rule out a false positive result.
 - ii) Detectable levels of marijuana in the drug screen are not exclusionary, if in the investigator's documented opinion the patient does not meet DSM-V criteria[15] for substance use disorder, in the investigator's documented opinion, the positive test does not signal a clinical condition that would impact the safety of the patient or interpretation of the study results.
3. Allergies and Adverse Drug Reactions
- a) History of drug or other allergy which, in the opinion of the principal investigator, makes the subject unsuitable for participation in the study
4. Sex and Reproductive Status
- a) Females of child-bearing potential who are unwilling or unable to use an acceptable contraceptive method or abstinence to avoid pregnancy for the entire study period and for 56 days after the study.
 - b) Women who are pregnant or breastfeeding. Women with a positive pregnancy test on enrollment or prior to study drug administration
5. ECG and Laboratory Test Findings
- a) Estimated glomerular filtration rate (eGFR) according to the re-expressed abbreviated (four-variable) Modification of Diet in Renal Disease (MDRD) Study equation $\leq 40 \text{ ml/min/1.73m}^2$
 - b) Corrected QT interval $> 470 \text{ msec}$ (QTc by method of Frederica), during the Screening/Baseline Phase
 - c) Left Bundle Branch block
 - d) Right Bundle Branch Block with a QRS duration $\geq 150 \text{ msec}$.

- e) Intraventricular Conduction Defect with a QRS duration \geq 150 msec.
 - f) Serum bilirubin (Total, Direct or Indirect) $>$ 1 x ULN (Only abnormal values of between 1-1.5x ULN may be repeated once for confirmation during the screening period.)
 - g) Neutrophil count \leq 1000/ μ L (or equivalent).
 - h) AST (SGOT) or ALT (SGPT) $>$ 1 x ULN (Only abnormal values of between 1-1.5x ULN may be repeated once for confirmation during the screening period.)
6. Other Exclusion Criteria
- a) Prisoners or subjects who are involuntarily incarcerated
 - b) Subjects who are compulsorily detained for treatment of either a psychiatric or physical (e.g., infectious disease) illness
 - c) Exposure to non-biological investigational agents (other than rimegepant) within the 30 days prior to Baseline visit.
 - d) Exposure to biological investigational agents within the 90 days prior to Baseline visit.
 - e) Score of $>$ 0 on the Sheehan Suicidality Tracking Scale for the period of 30 days prior to Screening and during the study.
7. Please see Section 5.4 for Prohibited medications and Section 5.4.1 for allowable Rescue Medications

5.4 Prohibited Concomitant Medication

The below medications are prohibited prior to randomization and during the course of this study or as specified.

1. St. John's Wort should not be taken 14 days prior to randomization and throughout the study.
2. Butterbur root or extracts should not be taken 14 days prior to randomization and throughout the study.
3. History of use of ergotamine medications on greater than/equal 10 days per month on a regular basis for greater than/equal 3 months
4. History of non-narcotic analgesic intake on greater than/equal 15 days per month for greater than/equal 3 months
5. Use of narcotic medication, such as barbiturates, heroin, opium in the form of morphine and codeine, oxycodone and hydrocodone for at least 2 days prior to randomization.
6. Use of acetaminophen or acetaminophen containing products at daily dosing levels greater than 1000mg/day for at least two days prior to randomization.
7. Use of marijuana is prohibited during the study.

Patients on prophylactic migraine medication are permitted to remain on therapy provided they have been on a stable dose for at least 3 months prior to study entry.

5.4.1 Rescue Medications

After dosing with study medication, all other headache medication is prohibited during the 2 hours post dose. However, a patient who does not experience relief of their migraine headache at the end of two hours after dosing with study medication (and after the two hour assessments have been completed on the eDiary), will be permitted to use the following rescue medication: aspirin, ibuprofen, acetaminophen up to 1000mg/day (this includes Excedrin Migraine) naprosyn (or any other type of non-steroidal anti-inflammatory (NSAID)), antiemetics (e.g., metoclopramide or promethazine), or baclofen. These are the only medications allowed for rescue treatment after 2 hours post dose of study medication. However, if needed, after 48-hours of administering the one dose of study medication (and before coming in for the End of Treatment Visit) patients may take their prescribed standard of care medications for treatment of migraine (including triptans if not contraindicated, **provided all of the assessments have been completed on the eDiary**). Similarly, if the migraine is relieved by study medication at 2 hours after dosing but then recurs to a moderate or severe intensity level between two and forty-eight hours, the patient will be permitted to take the same rescue therapy as outlined above. In all circumstances, the patient will always continue to complete his or her eDiary for up to forty-eight hours after consuming the study medication. Use of concomitant medication after randomization, including rescue medication, will be recorded by the patient on a paper diary and reported to the site. The site will record medications that were taken within 14 days of dosing with study medication (or until the End of Treatment Visit).

5.5 Women of Childbearing Potential

Women of childbearing potential (WOCBP) include any female who has experienced menarche and who has not undergone successful surgical sterilization (hysterectomy, bilateral tubal ligation, or bilateral oophorectomy) or is not postmenopausal. Post menopause is defined as:

1. Amenorrhea greater than or equal to 12 consecutive months without another cause and a documented serum follicle stimulating hormone (FSH) level > 35mIU/mL or
2. Woman with irregular menstrual periods and a documented serum follicle stimulating hormone (FSH) level > 35mIU/mL or

NOTE: FSH level testing is not required for women greater than or equal to 62 years old with amenorrhea of greater than or equal to one year

3. Woman on hormone replacement therapy (HRT)

Women of childbearing potential (WOCBP) and men must be using two acceptable methods of contraception to avoid pregnancy throughout the study and for up to 56 days after the last dose

of investigational product in such a manner that risk of pregnancy is minimized. It is required that all WOCBP use two methods of contraception for the duration of the study (i.e. beginning before treatment with the 1 dose of study medication to 56 days after dosing). The two methods should include one barrier method (ex. condom with spermicidal gel, intrauterine devices, cervical cap etc.) and one other method. The other method could include oral contraceptives or another barrier method (Note an Intra Uterine Device is considered one method).

Women who suspect that they have become or may have become pregnant despite using proper birth control methods, should use the home pregnancy test provided at Baseline Visit. Home pregnancy test should be administered prior to taking Investigational Study Drug. Patient should not take Investigational Study Drug if they are pregnant and patient should immediately contact Study Investigator.

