4.2 Study Schematic

4.3 Schedule of Assessments

Table 1: Schedule of Assessments

Procedure	Screening Visit (3-28 days)¹	Baseline Visit (Randomization)¹	Onset of moderate or severe migraine²	During Treatment 15, 30, 45, 60 and 90 minutes Post-Dose	During Treatment 2, 3, 4, 6, 8 hours Post- Dose	During Treatment 24 hours Post-Dose	During Treatment 48 hours Post- Dose	End of Treatment Visit
Eligibility Assessments								
Informed Consent	X							
Inclusion/Exclusion Criteria	X	X						
Medical History	X							
Prophylactic Migraine Medication/ Concomitant Medication ³	X	X						X
Assessment of Migraine History (Signs and symptoms) paper source ¹⁴	X							
Safety Assessments								
Physical Examination	X							X
Vital Signs/Physical Measurements ⁴	X	X						X
Clinical Safety Laboratory Testing ⁵	X							X

Procedure	Screening Visit (3-28 days)¹	Baseline Visit (Randomization)¹	Onset of moderate or severe migraine²	During Treatment 15, 30, 45, 60 and 90 minutes Post-Dose	During Treatment 2, 3, 4, 6, 8 hours Post-Dose	During Treatment 24 hours Post-Dose	During Treatment 48 hours Post-Dose	End of Treatment Visit
ECG	X							X
Pregnancy Test ⁶	X	X	X					X
Adverse Event and Serious Adverse Event Assessment ⁷	X	X	X	X	X	X	X	X
Sheehan Suicidality Tracking Scale ⁸	X	X						X
Clinical Drug Supplies/Study Supplies								
Randomize ⁹		X						
Dispense Study Medication		X						
Administer 1 dose of study medication ¹⁰			X					
Return unused study medication								X
eDiary returned/reviewed for completeness ¹¹								X
Efficacy Assessments¹²								
Assessment of migraine pain ¹³			X	X	X	X	X	

Procedure	Screening Visit (3-28 days)¹	Baseline Visit (Randomization)¹	Onset of moderate or severe migraine²	During Treatment 15, 30, 45, 60 and 90 minutes Post-Dose	During Treatment 2, 3, 4, 6, 8 hours Post-Dose	During Treatment 24 hours Post-Dose	During Treatment 48 hours Post-Dose	End of Treatment Visit
Assessment of Migraine Symptoms (photophobia, phonophobia, and nausea - eDiary) ¹³			X	X	X	X	X	
Functional Disability Scale ¹³			X	X	X	X	X	
MQoLQ (Migraine Specified Quality of Life Questionnaire) ¹³						X		
Preference of Medication ¹³						X		

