¹ **Screening/Baseline Phase** will be 3 - 28 days. The **Baseline Visit** may be scheduled but should only occur *after* all screening procedures are complete, patient meets inclusion/exclusion criteria, and lab test results have been received by the site.

² Patients will use eDiary to answer questions about their migraine symptoms upon experiencing a moderate/severe migraine headache. The patient will administer pre-dispensed study drug if 1) the headache remains moderate or severe; 2) the patient has completed all required migraine assessment questions in the eDiary, including their current most bothersome migraine symptom, and 3) the patient has not already taken prohibited medications (see protocol section 5.4).

³ Patients should keep track of their concomitant medications throughout the study and report them to the study personnel at the End of Treatment Visit. Any medication taken for recurrent headache should be documented. Use of concomitant medications after randomization, including rescue medications, will be recorded by the patient on a paper diary and reported to the site.

⁴ Height will only be captured at the Screening Visit. Weight body temperature, respiratory rate, blood pressure and heart rate will be collected at all time points where indicated. Sitting arterial systolic and diastolic blood pressure and pulse rate will be measured.

⁵ All Screening Visit laboratory test results must be received prior to Baseline Visit.

⁶ A serum pregnancy test will be completed at Screening and End of Treatment Visits as part of the standard laboratory tests (if appropriate). Confirmatory urine pregnancy test for WOCBP should be completed on site at Baseline Visit and any subsequent visits for confirmation at the Investigator's discretion. Home pregnancy test will be provided to WOCBP after completion of baseline visit.

⁷ SAEs are reported from the time of informed consent and non-serious AEs are reported from baseline. All ongoing non-serious AEs and SAEs will be followed to resolution or until investigator deems there will be no further status change. SAE and AE's that occur during the treatment period should be reported to the site.

⁸ This scale will be clinician administered, completed on site, and will be in paper. The source document will be provided by Biohaven. The assessment period for completing the scale will be 30 days prior to Screening, and since the last visit for the remainder of the study.

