- d) At the Baseline Visit prior to dispensing Investigational Study Medication, WOCBP must have a negative serum or urine pregnancy test (minimum sensitivity 25 IU/L or equivalent units of HCG)
- e) Women must not be breastfeeding

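### The pregnancy test scheduled at migraine onset is missing from the dosing conditions, and Section 5.5 does not make clear which women must take it

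*Protocol*

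**What the plan says.** **Texts that point to a test for every WOCBP at onset**

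- Protocol Section 4.3, Table 1: the row "Pregnancy Test" is marked at Screening, Baseline, onset of the moderate or severe migraine, and End of Treatment. SAP Appendix 3 carries the same marks.
- Protocol Section 6.2.4.2: pregnancy tests follow Table 1, and the home test is named as one of the methods.
- Protocol Section 5.5: "Home pregnancy test should be administered prior to taking Investigational Study Drug". The sentence names no group of women.

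**Texts that limit the test or leave it out**

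- Protocol Section 5.5, the sentence just before that one: "Women who suspect that they have become or may have become pregnant despite using proper birth control methods, should use the home pregnancy test".
- Table 1 footnote 6: "Home pregnancy test will be provided to WOCBP after completion of baseline visit". It does not say who must use the test, or when.
- Table 1 footnote 2: "The patient will administer pre-dispensed study drug if 1) the headache remains moderate or severe". Two further conditions follow, on completing the eDiary migraine questions and on not having taken prohibited medication. SAP Appendix 3 repeats this footnote.
- The dosing instructions in the Synopsis and in Sections 4.3.2 and 7.2.2 refer to pain intensity and eDiary steps, not to a pregnancy test.

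**Related safeguards**

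- Inclusion criterion 3d: "At the Baseline Visit prior to dispensing Investigational Study Medication, WOCBP must have a negative serum or urine pregnancy test".
- Exclusion criterion 4b covers "Women with a positive pregnancy test on enrollment or prior to study drug administration".
- Section 5.5 bars a pregnant woman from taking study drug and requires two methods of contraception.

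**The concern.** The tablet is taken at home, so the onset cell in Table 1 has effect only if the patient is told to test before she doses. The text that tells her when she may dose does not mention the test. The section that explains the home test opens by addressing only women who already suspect a pregnancy, and a test at onset is most useful for a pregnancy that is not suspected.

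What is at stake is fetal exposure to one dose of an investigational drug. The protocol otherwise treats this as something to prevent (exclusion 4b and the bar on dosing in Section 5.5) and to report within 24 hours if it occurs (Section 8.1.4). The efficacy analysis is not involved.

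**Working it through.** The plan gives no figure to reproduce. The check is a comparison of texts plus two intervals.

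**1. Which test can fill the onset cell?** Dosing is outpatient. Footnote 6 places the serum tests at Screening and End of Treatment and the urine test on site at visits. Only the home test remains.

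**2. Does any text make that test a condition of dosing?**

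- Footnote 2 has three conditions: pain still moderate or severe, eDiary questions answered, no prohibited medication. None is a test.
- Synopsis, 4.3.2 and 7.2.2: no test.
- Footnote 6: the kit is supplied, but its use is not required.
- Exclusion 4b acts on a positive result but does not say that a test must be done at onset.
- Section 5.5: the first sentence covers women who suspect pregnancy. The second gives the timing and no subject. The third bars dosing if pregnant. Read in order, the second sentence most naturally gives the timing for the women in the first. Read with Table 1 and Section 6.2.4.2, it can also mean every WOCBP.

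The last test that is clearly required to be negative before dosing is therefore the one at Baseline.

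**3. Longest gap from the Baseline test to the dose.** Study drug may be held for up to 45 days after randomization at Baseline (Section 4.3.2), so the maximum is 45 days.

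**4. Longest gap from the Baseline test to the next test if the onset test is skipped.** The End of Treatment visit falls within 7 days of treatment, with 2 further days allowed (Section 4.3.4): 45 + 7 + 2 = 54 days. That test comes after exposure.

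**5. How typical is the maximum?** Inclusion criteria 2c and 2e require 2 to 8 moderate or severe attacks per month. Taking a month as 30 days, the mean spacing between attacks is 30 / 2 = 15 days at the lower limit and 30 / 8 = 3.75 days at the upper. Most waits should be well short of 45 days.

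**6. How many women?** The documents give neither the share of subjects who are WOCBP nor a pregnancy rate under the required contraception. A count of untested exposures cannot be derived.

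**The case against.** The best case for the plan is that these texts form a single rule. The kit goes to WOCBP generally, the schedule marks the test at onset, Section 6.2.4.2 makes the schedule operative and names the home test, and the second sentence of Section 5.5 carries no condition of its own. On that reading every WOCBP must test before dosing, and an untested dose departs from study procedures. Footnote 2 also need not be a complete safety checklist, since it leaves out the bar on dosing in pregnancy, which plainly still applies.

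Much of this stands. A reader might infer that the protocol settles on testing only when pregnancy is suspected, or that it permits a WOCBP to dose untested. The documents do not support either statement: the universal reading is open, and silence in the dosing instructions does not cancel a scheduled test. Nor can one infer what women were actually told, because the consent pages were removed and the eDiary screens and kit instructions are not in these documents.

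The objection does not remove the inconsistency. If every WOCBP must test, the instruction that tells her when to dose omits a required step, and Section 5.5 opens with a sentence that suggests the step is for others. A woman could follow both in good faith and miss the test.

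**Conclusion.** The point holds as a minor participant-safety inconsistency. The schedule calls for a pregnancy test at onset, but the dosing conditions omit it and Section 5.5 is ambiguous about who must take it. A WOCBP with an unsuspected pregnancy who follows footnote 2 and the suspicion sentence could dose untested, at most 45 days after her negative Baseline test, and would next be scheduled for a test at most 54 days after Baseline.

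The risk is small. It involves one dose, after a negative Baseline test, with two contraceptive methods required and a standing bar on dosing if pregnant. The intervals are limits, and the attack-frequency criteria suggest that most waits are much shorter. No endpoint, analysis population or power figure depends on this.

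The conclusion rests on the wording of the two documents alone. A reader might infer that pregnant women were exposed, or that the safeguards fail as a whole. Nothing in the documents shows either.

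**What to change.** Two substantive edits:

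1. Section 5.5: add *Every WOCBP takes the supplied home pregnancy test at onset of the attack to be treated, before study drug, and records the result on the paper diary.* Keep the existing sentence for a woman who suspects pregnancy at an earlier time.
2. Protocol Table 1, footnote 2: add *4) for WOCBP, the home pregnancy test is negative.*

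Four places then follow as conforming edits only: the SAP Appendix 3 copy of footnote 2, the Synopsis, Section 4.3.2 and Section 7.2.2. Exclusion 4b needs no change.

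The kits are already on the list of study materials (Section 6.1), and patients already keep a paper diary for medications, so the addition there is one line. Each WOCBP does one urine test during a moderate or severe attack. A woman who cannot test would not dose for that attack, so dosing will occasionally be delayed or missed within the 45 days. A woman who used her kit earlier needs a replacement. The result remains self-reported.

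If the sponsor intends testing only on suspicion, marking the onset cell accordingly in both schedules would make the texts agree. It would leave the unsuspected pregnancy untested, so the first option is preferable.

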5.6 Other Restrictions and Precautions (if applicable)

Not Applicable

5.7 Deviation from Inclusion/Exclusion Criteria

Any significant event that does not comply with the inclusion exclusion criteria, study conduct, or study procedures will be documented as a deviation. Deviations will be documented and reported through the clinical monitoring of the trial. Deviations will be reported to the IRB/EC at the frequency required by your IRB/EC. There will be no protocol exceptions granted by the Sponsor for Inclusion/Exclusion criteria.

6 STUDY CONDUCT AND DESCRIPTION OF STUDY PROCEDURES

6.1 Study Materials

The following study materials will be provided at the study start:

- Investigator File/Regulatory Binder
- Pharmacy Binder
- Drug Accountability Logs
- Sample source documents, where applicable
- Concomitant and Rescue Medication Logs (take home for patient)
- Investigator Brochure
- Interactive Web-based Response System (IWRS)
- Electronic Case Report Form (eCRF) instructions
- Electronic Diary (eDiary): 1 will be given to each randomized patient
- Instructions for the ePRO device and access to the portal
- Laboratory Kits and Laboratory Manual
- Home Pregnancy Test
- ECG Machine and Instructions
- Serious Adverse Event (SAE) forms
- Pregnancy Surveillance Forms

All sites will use an Electronic Data Capture (EDC) tool to submit study data to Sponsors CRO. Electronic Case Report Forms (eCRFs) will be prepared for all data collection fields including Serious Adverse Events (SAE) Reporting. SAE data (including responses to queries) will be submitted to the CRO using eCRFs. Electronic Patient Reported Outcomes (ePRO) will be used for all patient-rated scales and will be captured on an eDiary. Any assessment completed by the patient in the eDiary will be transferred from the site/patient to the vendor and from the vendor to the CRO and/or sponsor. No additional source documents are required for scales and assessments completed by the patient in eDiary.

Safety laboratory, plasma, serum, instructions for all specimens collected will be provided by a designated central laboratory. ECG equipment, supplies, instructions and training materials will be supplied by a centralized ECG vendor.

